7.2.2	Monitoring procedures	39
7.2.3	Recording of data and retention of documents	39
7.2.4	Auditing procedures.....	40
7.2.5	Publication of results.....	40
7.2.6	Disclosure and confidentiality.....	40
7.2.7	Discontinuation of study	40
7.3	Ethics and Good Clinical Practice	41
7.3.1	Institutional Review Board/Independent Ethics Committee.....	41
7.3.2	Informed consent.....	41
7.3.3	Declaration of Helsinki	42
8	References (available upon request).....	43

List of tables

Table 3-1

Suggested schedule of assessments..... 21

List of abbreviations

ACTH	Adrenocorticotrophic Hormone
AE	Adverse Event
AESI	Adverse event of special interest
ALT	alanine aminotransferase
APTT	Partial Thromboplastin Time
AST	aspartate aminotransferase
ATC	Anatomical Therapeutical Chemical
b.i.d.	bis in diem/twice a day
BIPSS	Bilateral Inferior Petrosal Sinus Sampling
CD	Cushing's Disease
CI	Confidence Interval
CRF	Case Report/Record Form
CRH	Corticotrophin-Releasing Hormone
CRO	Contract Research Organization
DS&E	Drug Safety & Epidemiology
ECG	Electrocardiogram
EDC	Electronic Data Capture
ESE	European Society of Endocrinology
FDA	Food and Drug Administration
FPG	Fasting Plasma Glucose
GH	Growth Hormone
GIP	Glucose-Dependent Insulinotropic Polypeptide
GLP	Glucagon-Like Peptide 1
HbA1C	Hemoglobin A1C
ICH	International Conference on Harmonisation
IEC	Independent Ethics Committee
IGF-1	Insulin-like Growth Factor
IRB	Institutional Review Board
LDST	Low-Dose Dexamethasone Suppression Test
LOCF	Last Observation Carried Forward
MedDRA	Medical Dictionary for Drug Regulatory Activities
MRI	Magnetic Resonance Imaging
NYHA	New York Heart Association
PT	Prothrombin Time
QoL	Quality of Life
RAP	Report Analysis Plan
RBC	Red Blood Cells
REB	Research Ethics Board
RMP	Risk Management Plan
s.c.	sub-cutaneous
SAE	Serious Adverse Event
SAP	Statistical analysis plan
SI units	International system of units
SSA	Somatostatin Analogue
TSH	Thyroid Stimulating Hormone
UFC	Urinary Free Cortisol

ULN	Upper Limit Normal
WBC	White Blood Cells
WHO	World Health Organization
γGT	Gamma Glutamyl Transpeptidase

Amendments and updates

Number	Date	Section of study protocol	Amendment or update	Reason
1	20-Sep-2013	Sections 1, 2, 3, 6, 7 and 8	Amendment	Discussion with Health Authorities on data collection in large Cushing disease patient population treated with pasireotide s.c.
2		Sections 3, 6 and 7	Amendment	Modifications for publication of study results
				Update to lists and descriptions of adverse events
				Description of frequency of data transfers
3	06-May-2020	All document	Amendment	Change of Sponsorship from Novartis to Recordati
				Inclusion of IQVIA as CRO managing a number of study activities on behalf of Recordati

Amendment 3 (06 May-2020)

Amendment rationale

Novartis has signed an agreement to transfer the worldwide rights of Signifor® and Signifor® LAR to Recordati. Within the framework of such agreement, the two Companies agreed a sponsorship transfer of this study with pasireotide from Novartis to Recordati.

The purpose of this substantial amendment is to reflect the change in sponsorship, and to add IQVIA as the CRO in charge for performing some study-related activities on behalf of Recordati.

Changes to the protocol

Changes to specific sections of the protocol are shown in the track changes version of the protocol using strike through red font for deletions and red underline for insertions.

- All sections: were updated to substitute the name of the current sponsor Novartis with the name of the new sponsor Recordati or of IQVIA on behalf of Recordati, as applicable.

IRBs/IECs

A copy of this amended protocol will be sent to the Institutional Review Board (IRBs)/Independent Ethics Committee (IECs) and Health Authorities, as per local requirements.

The changes described in this amended protocol are substantial and do require IRB/IEC approval prior to implementation.

Amendment 2 (25-Jul-2016)

Amendment rationale

The purpose of this protocol amendment is to update the section on publication of study results. In addition, the description and list of adverse events of special interest (AESI) has been updated, and a list of special scenarios to the definition of adverse events (AE) has been added, in alignment with current program standards. Furthermore, the transfer of non-serious adverse events data to Novartis DS&E has been specified, i.e. to occur on a periodic basis but not less frequently than once a month. Few typographical errors were corrected and an incomplete sentence removed.

Patient enrollment in the study started in March 2013 and is planned to close in March 2021; the last patient's follow-up visit in the study is planned to be in April 2024. Due to the long duration of the study, publication of study results will not only occur upon study completion but be allowed at different timepoints throughout the study such as the yearly interim analyses. Furthermore, regional and/or local analyses and publications will also be allowed once analysis and publication of the overall population is performed.

Changes to the protocol

Changes to specific sections of the protocol are shown in the track changes version of the protocol using strike through red font for deletions and red underline for insertions.

List of abbreviations: updated with new abbreviations

Summary of previous amendments Amendment 1: addition of a sub-header

Section 3.5.2.1: The transfer of information on non-serious AEs to Novartis DS&E has been specified to occur on a periodic basis but not less frequently than once a month.

Section 3.5.2.1: Inclusion of a list of special scenarios that are also considered to be adverse events

Section 3.5.2.3: Updated description and list of AESIs

Section 3.5.2.4: Removal of incomplete sentence

Section 6.6: Updated to allow for additional interim analyses for regulatory or publication purpose

Section 7.2.5: Updated to allow for regional and/or local analyses and publications.

IRBs/IECs

The changes described in this amended protocol are non-substantial and do not require IRB/IEC approval prior to implementation.

Summary of previous amendment(s)

Amendment 1

Amendment rationale

This amendment has been implemented based on discussion with Health Authorities. It addresses the following key items of the original protocol released for the study:

Pasireotide s.c. is being made available in several countries. As it is the first approved medication targeting the underlying cause of Cushing's disease, there is a growing interest to follow-up patients treated with the compound. Therefore, one of the main reasons to issue the amendment is to collect data in a large patient population affected by Cushing's disease. As a consequence this study will enroll up to 200 patients but not less than 100 patients.

Furthermore, more disease specific background information on potential risk factors for hyperglycemia, liver-related adverse events, QT prolongation, atypical infections and adrenal insufficiency will be collected. This information is related to some adverse drug reactions recorded during the treatment with pasireotide.

Even though this is an observational trial, the experience with the medication is still limited to clinical trials. Therefore, it is considered very useful to provide a list of suggested schedules of assessments that can help the investigator following up the patients treated with pasireotide. This would lead to a more consistent approach to the use of the medication.

Since the enrollment target should primarily be based on new users (pasireotide naïve patients starting treatment with pasireotide s.c. on the day of inclusion into the study), and based on the fact that pasireotide s.c. is already available in many countries by the time of study implementation it is considered challenging to enroll pasireotide naïve patients, the enrollment period was extended to 96 months.

In order to ensure patients' safety and completeness of study data a follow-up period of 3 months will be implemented for patients lost to follow-up. The investigator is requested to show "due diligence", for the first 3 months after the last known date the patient took pasireotide, by documenting in the source documents steps taken to contact the patient, e.g. evidence of two certified letters, dates of telephone calls, sent emails.

Specific Health Authorities require reporting of non-serious adverse events on a monthly basis. Therefore, the protocol requires investigators to update the electronic case report form at least once a month so that the database reflects most up-to-date safety information once per month.

SAEs should be collected even if they may be related to the underlying condition. Analyses and careful interpretation of data should allow for the possibility of relationship of the SAE to the underlying condition. Therefore, the following event will be removed from the events not considered to be serious adverse events for hospitalizations: "hospitalization for any SAEs that are expected due to the condition being treated, including if the SAE is a primary outcome measure, and whether there has been a clear agreement with regulators not to consider these as SAEs, provided the information is collected elsewhere"

In order to ensure consistent reporting of adverse events the protocol requires adverse event reporting according to CTCAE version 3.0.

Data will be summarized and displayed by time intervals based visit windows rather than by a strict visit schedule.

A Full Analysis Set (FAS) has been defined.

Incidence rates by person-time of exposure and person-time of observation will be reported.

Missing data handling has been described in more detail.

Further clarification on sample size and power considerations have been provided.

Minor discrepancies have been corrected and additional minor information has been added on the statistical hypothesis, model and method of analysis.

As of the release date of this amendment, 5 patients have been enrolled in this study. There is an anticipated impact of this amendment on the duration of recruitment and on the release of results.

Changes to the protocol

Changes to specific sections of the protocol are shown in the track changes version of the protocol using strike through red font for deletions and red underlined for insertions.

The major changes to the protocol, and the sections affected, are detailed below.

List of abbreviations

- EMA (European Medicines Agency) removed from the list of abbreviations as long term safety follow-up study has been requested by additional Health Authorities and study is applicable to more than one geographic region.
- 1. Introduction
 - “EMA” has been replaced by Health Authorities.
- 2.2.1 Endpoints for secondary objectives
 - Clarification that change from last dose will be evaluated for all available “continuous” safety and efficacy parameters
- 3.1.1 Safety and tolerability assessments
 - Redundancy was removed from this section “for all available parameters”
 - Removal of request for regular monitoring and recording of safety data as this has now been described in the suggested table of assessments
 - Addition of recommendation to report data on history of smoking, history of alcohol use, and presence of hepatitis B and C infection in medical history
- 3.1.2 Efficacy assessments
 - Redundant text “for all available parameters” removed

- 3.3.1 Patient Population
 - Country and site number increased as this long term safety follow-up study has been requested by additional Health Authorities outside of Europe and new requirement of including patients starting pasireotide s.c. at time of enrollment has been added. Timelines and number of patients to be included has been updated as well.
- 3.4.1.1 Treatment discontinuation
 - Clarification that Patients who discontinue pasireotide s.c. treatment because of an adverse event, must be followed by the investigator until resolution of the AE or until 3 months following discontinuation of drug whichever is longer.
 - Addition of details on “lost to follow-up” procedure such as requirement of two certified letters, telephone call and emails.
- 3.4.1.2 Medical history and prior/concomitant treatment of Cushing’s disease
 - Addition of recommendation to report data on history of smoking, history of alcohol use, and presence of hepatitis B and C infection in medical history
- 3.5 Visit Schedule and Assessments
 - “Suggested schedule of assessments” has been included in protocol to help encourage more uniform data collection across study sites and patients. 3.5.2.1 Adverse events
 - 3.5.1 Patient demographics and other baseline characteristics
 - Addition of recommendation to report data on history of smoking, history of alcohol use, and presence of hepatitis B and C infection in medical history
 - 3.5.2.1 Adverse events
 - Addition of further details of adverse event reporting
 - Addition of requirement of reporting adverse events according to the Common Toxicity Criteria for Adverse Events (CTCAE) version 3.0
 - 3.5.2.2 Serious Adverse events
 - Removal of event from the events not considered to be serious adverse events for hospitalizations: “hospitalization for any SAEs that are expected due to the condition being treated, including if the SAE is a primary outcome measure, and whether there has been a clear agreement with regulators not to consider these as SAEs, provided the information is collected elsewhere”
 - Addition of details on adverse events of special interest for pasireotide s.c.
 - 3.5.3.1 Laboratory evaluations
 - In order to ensure availability of baseline for UFC efficacy parameter for patients who did not have an UFC assessment at their first visit requirement of entering the last available UFC value before study entry will be collected on the CRF.

- 6 Statistical methods
 - Clarification that data will be summarized and displayed by time intervals based visit windows rather than by a strict visit schedule
 - Clarification that for patients who discontinue treatment prior to the 3-year observation period, their safety and efficacy parameters will be reported according to the time window that corresponds to Day of last dose of pasireotide s.c 90 days.
 - Clarification that continuous variables will be summarized by number of patients, mean, standard deviation, minimum, median and maximum. Categorical variables will be summarized by absolute and relative frequencies. Counts of missing values for both continuous and categorical variables will be reported. Results with and without imputation will be reported.
- 6.1.1 Full Analysis Set (FAS)
 - Definition of Full Analysis Set added
- 6.2 Patient demographics/other baseline characteristics
 - Clarification that counts of missing values for both continuous and categorical variables will be reported
- 6.3 Treatments (pasireotide s.c, concomitant therapies)
 - Clarification that treatment includes prescribing information on the pasireotide s.c. start and stop dates, dose, dose changes and reason for changes
 - Clarification that incidence rates by person-time of exposure and incidence rates by person-time of observation with their corresponding 95% confidence interval will be reported.
- 6.4.2 Statistical hypothesis, model, and method of analysis
 - Clarification that the study is exploratory in nature and no formal hypothesis testing is planned
- 6.5.1 Efficacy evaluation
 - Clarification that the efficacy analysis will be performed on the FAS
 - Deletion of “Incidence of Adverse events...” efficacy endpoint as this constitutes a safety endpoint
- 6.5.1.2 Absolute and percentage change from baseline secondary efficacy endpoints
 - Deletion of LOCF method
- 6.5.1.3 Absolute change between the last assessment on drug and 3 months later for continuous secondary efficacy endpoints added
 - New header added
- 6.5.1.5 Handling of missing data
 - New paragraph added

- 6.5.2 Safety evaluation
 - Clarification that for all safety analyses the safety set will be used
 - Clarification that for continuous safety variables, the change from the last dose of pasireotide s.c. to 3 months after permanent discontinuation of pasireotide s.c. for patients that discontinue pasireotide s.c. prior to completing the 3-year observation period will be summarized.
 - Clarification that safety analysis will be stratified by incident or prevalent use of the drug.
- 6.5.2.2 Laboratory evaluations
 - Clarification that no imputations for missing values will be done for laboratory variables and they will be identified as missing
- 6.5.2.3 Other safety data
 - Clarification that no imputations for missing values will be done for laboratory variables and they will be identified as missing
- 6.5.3 Subgroup Analysis
 - Clarification that subgroup analysis will be performed for other countries than Germany on request.
- 6.6 Interim Analyses
 - “EMA” replaced by Health Authorities.
 - Clarification that analysis of study will occur when all patients complete the study.
- 6.7 Sample size and power considerations
 - Enrollment information updated
- 7.1.3 Instructions for completing adverse event case report forms
 - Section deleted as information of this chapter has been added to section 3.5.2.1
- 8 References
 - Reference for Common Toxicity Criteria for Adverse Events (CTCAE) version 3.0 has been added.

The term “trial” has been replaced by “study” across the entire protocol.

IRBs/IECs

A copy of this amended protocol will be sent to the Institutional Review Board (IRBs)/Independent Ethics Committee (IECs) and Health Authorities according to local requirements.

The changes described in this amended protocol may require IRB/IEC approval prior to implementation according to local regulation. In addition, if the changes herein affect the Informed Consent, sites may be required according to local regulation to update and submit for approval a revised Informed Consent that takes into account the changes described in this amended protocol.

1 Introduction

Cushing's disease (CD) is a devastating endocrine disease that is caused by an adrenocorticotrophic hormone (ACTH) secreting pituitary adenoma. Epidemiological studies indicated an annual incidence of 0.7-2.4 per million population ([Lindholm et al 2001](#)). However, a recent study performed in Belgium reported a much higher prevalence of CD ([Daly et al 2006](#)): 55 per million population. Eighty percent of these tumors can be classified as microadenomas, and 20% as macroadenomas. The elevated ACTH levels secreted by these tumors stimulate the adrenal glands to produce excess cortisol, leading to the subsequent development of the clinical signs and symptoms of hypercortisolism. Cushing's disease is rare, associated with severe morbidity and premature mortality and most commonly affects adults aged 20-50, primarily females. Patients suffer from this disease for many years before coming to medical attention and appropriate diagnosis.

The most common pathological finding in these patients is bilateral hyperplasia of the adrenal cortex due to excessive ACTH secretion. The primary clinical symptoms of Cushing's disease are due to hypercortisolism, and include the following:

- Change in body habitus: moon face, supraclavicular fat pad, buffalo hump
- Hirsutism on face, neck, chest, abdomen, thighs
- Skin changes with easy bruising, purplish striae, reddening of the cheeks due to weakened connective tissue
- Generalized weakness and fatigue
- Wasting of musculature, particularly proximal muscles
- Menstrual disorders in females
- Decreased fertility and/or libido
- Hypertension
- Weight gain
- Diabetes mellitus
- Depression, mood and behavior disorders
- Sleep disturbances
- Osteopenia/osteoporosis

Most patients also develop a high set-point for feedback inhibition of ACTH secretion by cortisol. In addition to the patient's medical history and physical examination, several laboratory tests and diagnostic techniques are available for the diagnosis of Cushing's disease. Twenty four hour urinary free cortisol (UFC) measurements, blood sampling for serum cortisol levels, and the low-dose dexamethasone suppression test (LDDST) are widely used as screening tests for the diagnosis of Cushing's disease ([Newell-Price et al 1998](#)). To distinguish Cushing's disease from other forms of hypercortisolism, a confirmation of a pituitary source of ACTH secretion is needed. This includes an inappropriately normal or elevated plasma ACTH level and evidence of pituitary tumor on magnetic resonance imaging (MRI) scan or confirmed by bilateral inferior petrosal sinus sampling (BIPSS) after corticotrophin-releasing hormone (CRH) stimulation test (evidence of a pituitary source of ACTH). It is generally accepted that if the ratio of adrenocorticotrophin concentration in the inferior petrosal sinuses to peripheral

blood is greater than or equal to 3.0 after CRH stimulation, a diagnosis of Cushing's disease can be made ([Oldfield et al 1991](#)).

Pituitary resection of the adenoma is the current first-line therapy for Cushing's disease, but surgical failure rates are as high as 25-30% even in the hands of the most experienced neurosurgeons. Additionally postoperative recurrence rates are as high as 20% by 5 years ([Bochicchio 1995](#), [Sonino 1996](#)). Surgery is in many cases complicated by hypopituitarism, which requires complicated life-long hormonal replacement therapy necessary to sustain life. Treatment usually focuses on replacing the target hormones rather than the pituitary hormones, and in patients who have multiple axis deficiencies maintenance with multiple replacement hormones can be difficult, and requiring close and constant medical monitoring, and can be expensive ([Swearingen et al 1999](#)).

Irradiation of the pituitary is another option but it may take many years to be effective and it is curative in only 15 to 45% of the cases. In addition, due to its lack of specificity the procedure also often results in hypopituitarism. Furthermore, there is a 1 to 2% risk of development of secondary tumors in the field of radiation over subsequent years ([Orth 1995](#)).

When surgery and/or irradiation fail, or for those patients for whom such therapies are not an option, the remaining alternative is pharmacological treatment. No drug is currently approved for the treatment of Cushing's disease and the ones which physicians are using are fraught with suboptimal results and significant side effects ([Miller 1993](#), [Nieman 2002](#)) preventing their long term use required in the management of CD. Therefore, a safe and effective targeted medical therapy is highly desirable in this patient population.

Pasireotide (SOM230) is a novel cyclohexapeptide, somatostatin analogue. Pasireotide exhibits a unique binding profile with high affinity to four of the five known human somatostatin receptor subtypes (sst1, 2, 3 and 5).

A phase III [CSOM230B2305] study evaluated the efficacy and safety of two doses of pasireotide s.c. (600 and 900 μ g s.c. b.i.d., respectively) in 162 patients with moderate to severe Cushing's disease by evaluating the normalization of UFC values at 6 months of treatment. The study showed that pasireotide is an active medication in the treatment of hypercortisolism in CD. At month 6, 26.3% of patients who were randomized to pasireotide 900 μ g b.i.d. were considered to be responders (patients with a mean UFC \leq ULN, who did not up-titrate the dose during the 6-month treatment period). In the 600 μ g b.i.d. dose group, 14.6% of patients were responders. The mean UFC decreased in both treatment groups. The mean absolute change from baseline in mean UFC were -463.4 and -363.9 nmol/24h respectively for the 600 μ g and 900 μ g b.i.d. groups (which represent a median decrease from baseline of approximately 47% in both study groups). Overall, as mean UFC decreased continuous measures of the signs of Cushing's disease (blood pressure, weight and serum lipid levels) improved. Overall pasireotide was well tolerated. The majority of the AEs reported are consistent with the known adverse drug reactions of SSAs. The most commonly affected system organ classes were gastrointestinal disorders, general disorders, and metabolism and nutrition disorders. The most frequent AEs were diarrhea, nausea and hyperglycemia. As expected in successful therapies for hypercortisolism, adverse events related to cortisol withdrawal (hypocortisolism) were reported in some patients, for which a dose decrease resulted in effective management of the AE.

However, study durations are limited and long-term efficacy and safety is also limited. The pasireotide-induced effects of long-term hyperglycemia and other potential long-term effects (i.e. on GH/IGF-1 axis) could not be addressed by the pivotal trial [[CSOM230B2305](#)]. As Health Authorities require such data, the purpose of this non-interventional study is therefore to generate long term safety and efficacy data during the long-term treatment of pasireotide s.c. in patients with Cushing's disease in a real life setting.

2 Study objectives

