## 5 HANDLING OF MISSING DATA AND OUTLIERS

### 5.1 AE date imputation

Partial adverse event start dates are imputed with reference to the treatment start date. Completely missing start dates will not be imputed.

Any missing onset date, causality, or severity must be queried for resolution. Unsolved missing values will be imputed according to the following:

AE start date imputation:

1. If the AE start date year value is missing, the date uncertainty is too high to impute a rational date. Therefore, if the AE year value is missing, the imputed AE start date is set to NULL.
2. If the AE start date year value is less than the treatment start date year value, the AE started before treatment. Therefore:
  - a. If AE month is missing, the imputed AE start date is set to the mid-year point (01JulYYYY).
  - b. Else if AE month is not missing, the imputed AE start date is set to the mid-month point (15MONYYYY).
3. If the AE start date year value is greater than the treatment start date year value, the AE started after treatment. Therefore:
  - a. If the AE month is missing, the imputed AE start date is set to the year start point (01JanYYYY).
  - b. Else if the AE month is not missing, the imputed AE start date is set to the later of (month start point (01MONYYYY), AE start reference date + 1 day).
4. If the AE start date year value is equal to the treatment start date year value:
  - a. And the AE month is missing the imputed AE start date is set to the AE reference start date + 1 day.
  - b. Else if the AE month is less than the treatment start month, the imputed AE start date is set to the mid-month point (15MONYYYY).
  - c. Else if the AE month is equal to the treatment start date month or greater than the treatment start date month, the imputed AE start date is set to the later of (month start point (01MONYYYY), AE start reference date + 1 day).

AE end date imputation:

1. If the AE end date month is missing, the imputed end date should be set to the earliest of the (treatment follow up period date, 31DECYYYY, date of death).
2. If the AE end date day is missing, the imputed end date should be set to the earliest of the (treatment follow up period date, last day of the month, date of death).
3. If AE year is missing or AE is ongoing, the end date will not be imputed.

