If complete (imputed) AE end date is available and the imputed AE start date is greater than the (imputed) AE end date, then imputed AE start date should be set to the (imputed) AE end date.

---

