4. If imputed CM end date is less than the CM start date, use the CM start date as the imputed CM end date.

---

- If complete (imputed) CM end date is available and the imputed CM start date is greater than the (imputed) CM end date, then imputed CM start date should be set to the (imputed) CM end date.

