Post-treatment AEs and post-treatment SAEs will be summarized by primary SOC, PT and maximum CTC grade in patients who discontinued pasireotide s.c. prior to completing the 3- year observation period.

In addition, (S)AEs leading to study discontinuation will be listed. Note that there is no respective flag on the eCRF. Therefore the listings will show all (S)AEs which were ongoing at the time of study discontinuation due to AE or which ended the day before.

Also summary on clinically notable AEs (patients who had grade 3/4 AEs, SAEs, AEs leading to discontinuation or other significant AEs) will be prepared for the subgroup of patients from German sites.

Specific groupings of AEs of special interest will be considered and the number of patients with at least one event in each grouping ("category") will be reported. Such groups consist of AEs for which there is a specific clinical interest in connection with pasireotide treatment (i.e. where pasireotide may influence a common mechanism of action responsible for triggering them) or AEs which are similar in nature (although not identical) within project defined group. The specific groupings of AEs as defined in the Attachment 9.2 AESI List (latest documentation available prior to database lock) will be used.

The following tables will be produced:

- AEs of special interest, regardless of relationship with pasireotide s.c., by category, preferred term and maximum CTC grade,
- SAEs of special interest, regardless of relationship with pasireotide s.c., by category, preferred term and maximum CTC grade,
- AEs of special interest, regardless of relationship with pasireotide s.c., by type (any AE, AE suspected to be related to pasireotide s.c., SAE, AE leading to discontinuation, AE requiring dose adjustment or study-drug interruption) and PT

---

Study Code: CSOM230B2410

- AEs of special interest, regardless of relationship with pasireotide s.c., by time interval of onset (0 to < 3 months, 3 to < 6 months, 6 to <9 months, etc.), category and preferred term.

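### SAP 5.1 caps a partly known AE end date at an undefined follow-up date, so an AE that resolved late can be dated as ending before its own recorded month or year

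*Protocol*

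**What the plan says.** **Follow-up of AEs.** Protocol 3.4.1.1 requires that patients who stop the drug because of an AE "must be followed by the investigator until resolution of the AE or until 3 months following discontinuation of drug whichever is longer". Protocol 3.5.2.1 requires any detected AE to be followed until it resolves or is judged permanent.

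**End dates.** For an end date known only to the month, SAP 5.1 reads: "the imputed end date should be set to the earliest of the (treatment follow up period date, last day of the month, date of death". If the month is also missing, the end date is the "earliest of the (treatment follow up period date, 31DECYYYY, date of death". The same section adds: "If AE year is missing or AE is ongoing, the end date will not be imputed". SAP 4.1 likewise reports AEs without a documented end date as continuing. The *treatment follow up period date* is not defined anywhere in the SAP.

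**Start reset.** If an imputed start is later than the complete or imputed end, "then imputed AE start date should be set to the (imputed) AE end date".

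**Where the dates are used.** The on-treatment period runs to 28 days after last dose (SAP 8.4). AEs are collected to 90 days after last dose in patients who discontinue early, and to 28 days in those who complete (SAP 8.4.1). There is no CRF flag for AEs leading to study discontinuation, so that listing shows "all (S)AEs which were ongoing at the time of study discontinuation due to AE or which ended the day before". AE outcome is not on the AE CRF pages (SAP 6.1.1).

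**The concern.** The protocol expects some AEs to resolve after treatment follow-up has ended. The SAP's minimum rule then replaces a recorded end month or year with an earlier date that contradicts what the site entered. Because AE outcome is not captured on the AE pages, the end date carries the information on resolution. The discontinuation listing is also selected on it, so an event that was still active at study exit could be left out.

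The reset rule adds a second risk. If the cap falls at the end of the on-treatment period, an imputed start can be pulled back to that day. The AE would then move into the treatment-emergent tables, including the primary related-AE summary where the investigator suspected a relationship. It would also enter the numerator of the exposure-adjusted rates (SAP 6.2.4), and in an early discontinuer it would leave the post-treatment table.

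**Working it through.** The plan gives no figure on this point, so there is none to reproduce. The check applies the SAP 5.1 rules to hypothetical dates.

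**Inputs.** Imputed end = min(follow-up date F, last day of recorded month or year, death). F is undefined, so it is taken as last dose + 28 (the safety gap in SAP Table 6-2), as last dose + 90 (the post-discontinuation period), or removed. Where the treatment start is in an earlier month, a start lacking its day becomes the first of its recorded month. An AE counts as treatment-emergent here if its final start is on or before last dose + 28.

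**Patient A:** last dose 15 May 2019; + 28 = 12 June 2019; + 90 = 13 August 2019. **Patient B:** last dose 10 January 2018; + 28 = 7 February 2018; + 90 = 10 April 2018.

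| AE as recorded | F = + 28 | F = + 90 | No cap |
|---|---|---|---|
| A1: 10 May 2019 to NOV2019 | end 12 June | end 13 August | end 30 November |
| A2: JUL2019 to JUL2019 | end 12 June; start reset from 1 July to 12 June | 1 July to 31 July | 1 July to 31 July |
| B1: 20 March 2018 (complete) to MAY2018 | end 7 February | end 10 April | end 31 May |

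**Late resolution (A1).** From 12 June to 1 November is 142 days; from 13 August to 1 November is 80 days. Under either reading the imputed end lies before the recorded month begins. The AE is treatment-emergent in every column; only its end moves.

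**Discontinuation listing (A1).** Suppose the patient left the study because of this AE and the listing is programmed on imputed dates. The event stays listed only if its end is no earlier than the day before exit. With F = + 28 it is lost for an exit on or after 14 June; with F = + 90, on or after 15 August.

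**Change of class (A2).** The imputed start of 1 July is 47 days after last dose, hence post-treatment. With F = + 28 the imputed end (12 June) precedes it, the reset applies, and the AE becomes treatment-emergent. With F = + 90 nothing moves.

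**Complete start (B1).** With F = + 28 the end falls 41 days before the known start (7 February to 20 March). The reset is written for imputed starts only, so the AE stays post-treatment with an impossible end date. With F = + 90 the end follows the start but is 21 days before 1 May.

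**Illustration over many dates.** 40,000 hypothetical AEs, with true onset uniform on days 29 to 90 after last dose, duration uniform on 1 to 120 days and calendar dates spread at random; share classed treatment-emergent:

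| Start / end known to | No cap | F = + 28 | F = + 90 |
|---|---|---|---|
| month / month | 23.8% | 100% | 23.8% |
| year / month or year | 91.4% | 100% | 91.4% |
| day / month or year | 0% | 0% (100% end before start) | 0% |

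The no-cap column comes from the start-date rule alone and is a separate matter. The 100% entries follow from the construction: every true onset is after day 28 and the cap sits on day 28. They show what the rule does, not how often it will act.

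**The case against.** Several points on the other side stand.

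- A reader might infer that unresolved AEs will appear resolved. The documents do not support this: ongoing AEs get no imputed end, and a partial end date means that the site recorded an end. What is wrong is the timing.
- A reader might infer that post-treatment AEs will generally become treatment-emergent. That needs a + 28 cap and partial dates at both ends. SAP 8.2.1.2 and 8.2.1.4 treat the 90 days after last dose as a follow-up period, which favours + 90 for early discontinuers, and a + 90 cap moves no AE into the on-treatment period. The + 28 reading is plausible at least for patients who complete 3 years, whose AE collection ends then. In them, later events should be few: Protocol 3.5.2.2 asks only for SAEs with a suspected relationship.
- AEs that stop the drug normally begin on treatment and are already treatment-emergent. Protocol 3.4.1.1 therefore supports the end-date error, not the change of class.
- SAP 5.2 looks like a safer model, because it says "If imputed CM end date is less than the CM start date, use the CM start date as the imputed CM end date". But 5.2 goes on to give the same start reset for medications, so it is not a clean contrast.
- SAP 6.1.4 would date A1's end to 1 November, but only to derive the last contact date. It is not a competing AE end date.
- No analysis of AE duration or time to resolution is planned, and SAP 5.1 requires missing onset dates to be queried first.

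These points narrow the consequences. They do not remove the rule that overwrites a recorded month or year with an earlier date.

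**Conclusion.** The point holds in a limited form. As written, SAP 5.1 dates an AE whose recorded end month or year lies wholly after the cap as ending before that period, under both the + 28 and the + 90 reading (142 or 80 days before the recorded month in the example). Such an AE can be lost from the discontinuation listing, depending on the exit date and on the listing using imputed dates.

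Reclassification as treatment-emergent is conditional on a cap at last dose + 28 and on partial start and end dates. With a complete start, the same cap can instead produce an end before the start. The number of AEs with partial dates is not given, so no overall effect on the primary summary can be stated. This is a stated rule that gives a wrong date, not a missing detail, and it is cheap to correct.

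**What to change.** In SAP 5.1, delete the *treatment follow up period date* from both end-date rules. Impute a partial end as the last day of its recorded month, or 31 December of its recorded year, limited only by death. It should never be earlier than the first day of the recorded period or than a complete AE start date. A death date before the recorded end period should be queried.

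Keep the start reset for imputed starts. Once the cap is gone, it correctly handles AEs that ended before treatment. For example, with treatment start 15 May 2019 and an AE recorded as 2019 to MAR2019, start rule 4a gives 16 May (taking the reference date as treatment start), the end is 31 March, and the reset moves the start to 31 March. Setting the end equal to the start, or limiting the reset to complete end dates, would turn this pre-treatment AE into a treatment-emergent one.

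Cost: a small text and programming change, with no new data. Some AEs will show later end dates.
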